In general, these variables will be described and modeled similarly to secondary outcomes, to potentially support future research. Hypothesis testing results, if obtained, will be interpreted descriptively and not to claim benefit or harm on the basis of CYCLE II data. The distributions of patient-reported falls within the course of the study year across patients within each treatment group will be assessed for compatibility with Poisson distribution. If, as is anticipated, overdispersion is observed, then the negative binomial or other models for overdispersed count data will be entertained.

Adverse events

Adverse events will be descriptively tabulated and compared by Common Terminology Criteria for Adverse Events (CTCAE) system/organ class and preferred term. Serious adverse events will be similarly tabulated and described in individual listings including calendar date and interval from randomization, severity grade (1-5), current status, and assessed relatedness to the exercise intervention. Serious adverse events related to the intervention are expected to be few, and formal hypothesis testing will not be performed due to anticipated low statistical power and the multiple testing context.

Effect modification/subgroup analyses

For those outcomes for which a statistically significant effect of the intervention is found, we will examine statistical interactions of the randomized aerobic exercise regimen with study site, age, sex, BMI, employment status, patient-reported intensity of regular pre-study exercise, primary Parkinson's disease symptoms, primary Parkinson's disease symptom, years since Parkinson's disease diagnosis, whether or not the patient reports any falls during the pre-study year, and baseline MDS-UPDRS III value. For potential categorical effect modifiers, we will focus on an overall Wald test rather than p-values for comparisons of specific subgroups. For continuous variables, we will focus on linear interactions. If a linear interaction is detected, however, we will also assess possible nonlinearity in models using restricted cubic spline effects, and we may also choose to reexpress and communicate the effect in terms of categories defined by ranges to better communicate clinical relevance.

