Participant Recruitment, Screening and Randomization:

CC's Center for Neurological Restoration (CNR) manages 6,000+ PD patients; each patient typically has semi-annual neurology visits which include a complete MDS-UPDRS III evaluation. UU's Movement Disorders Program manages 2,000+ PD patients. Their respective Directors, Drs. [name] (Cleveland) and [name] (Utah), will lead their medical teams to screen in recruiting for this project and will complete MDS-UPDRS III clinical evaluations, blinded to group assignment. The pragmatic clinical trial design, with exercise at home and relatively few visits to the study site, will minimize travel burden, easing recruitment and facilitating recruitment of a racially and socio-economically diverse patient group.²³ It is anticipated that study sites will enroll an equal number of participants. Adults with idiopathic PD who meet inclusion criteria and cleared for exercise will

be randomized to either the home exercise or UCC group, using a permuted block randomization stratified by site, with random block sizes of 8, 10, or 12 for the first 8 blocks at each site, and 4, 6, or 8 subsequently, preloaded into a secure and shared RedCap electronic data management system developed at CC. Both sites have effectively utilized RedCap across in previous multi-site clinical trials,²⁴⁻³¹ and clinical programs. Figure 1 depicts study flow. Total study participation time is projected to be 12.5 months, including ~2.5 weeks for cycle delivery and completion of initial Comprehensive Assessments (On-/Off- meds).

As shown in Figure 1, three Comprehensive assessments of motor and non-motor function will be conducted for all participants. Comprehensive (90 mins) assessments (Table 1) will be overseen by Drs. [name] and [name], and will be completed at project enrollment (On- and Off-medication), 6 months (Off-medication), and 12 months (Off-medication). Visit windows will be within \pm 10 days of their nominal dates. Participants will be reimbursed for time and travel expenses of \$50 for each assessment. All clinical and self-report data will be entered into the RedCap database (see Data and Safety Monitoring). Each site's biomechanical data from the iPad will be uploaded securely, with encryption, to the CC HIPAA-compliant cloud instance (ClearData), processed in the cloud, and integrated into the [name] lab's on-premises, firewall protected, server.

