Title: Pragmatic Cyclical Lower Extremity Exercise Trial for
Parkinson's Disease

NCT#: NCT04000360

Document Date: January 29, 2024

The Cyclical Lower Extremity Exercise for Parkinson Disease II (CYCLE-II) Study
Principle Investigator: [name].
Site Principal Investigator: [name].

Statistical Analysis Plan: Assessment of Treatment Effect
Study Statistician: [name].

Overview

CYCLE-II is a pragmatic two center, blinded examiner, 1:1 randomized clinical trial to assess whether one year of a home Peloton-cycle based aerobic exercise regimen alters Parkinson's disease progression from that of patients receiving usual care and usual physical activity. The trial is conducted at the Cleveland Clinic and the University of Utah, coordinated by the former. The CYCLE-II study design and basic analytic plan have been published (*Phys Ther* 2021 Nov; 101(11):pzab191, PMCID: PMC8632855). Multiple prespecified quantitative outcomes are hierarchically classified as primary inferential, secondary inferential, and descriptive exploratory outcomes, and assessed in randomly ordered on and off Parkinson's medication examinations at baseline, and again off medication at six and 12 months. Parkinson's disease progression is to be assessed in each group by the estimated annual rates of change of off-medication outcome measures, and the treatment groups are to be compared in intention-to-treat analyses of these estimates.

Study Outcomes

The primary outcome is the total score on the Movement Disorder Society Unified Parkinson's Disease Rating Scale Part III: Motor Examination, an assessment of the motor signs of Parkinson's disease by an examiner masked to the participant's treatment group. Secondary inferential motor outcomes are:

- i. Upper extremity dexterity: time to complete a iPad-based modification of the Nine Hole Peg Test;
- ii. Lower extremity functional mobility
 - a. time to complete an iPad-instrumented Time Up and Go Test;
 - b. average turn velocity on an iPad-instrumented Time Up and Go Test;
- iii. Ambulation gait speed
 - a. average "comfortable speed" velocity on the Ten Minute Walk Test;
 - b. average "fast speed" velocity on the Ten Minute Walk Test;

Secondary non-motor outcomes are:

- i. Neural processing speed: number correct on the New Processing Speed Test;
- ii. Episodic visual memory: Number of locations + number of symbols correctly recalled on the New Symbol Modalities Test;

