The distributions of baseline variables will be summarized, overall and by treatment group, by frequency distribution for dichotomous and other categorical factors, mean and standard deviation for reasonably symmetrically distributed quantitative variables, and Tukey five-number summaries (median, quartiles, extrema) for substantially skewed variables. We will also examine boxplots, histograms and kernel density estimators for continuous variables, and use standardized mean differences for continuous variables and categories of nominal and ordinal variables to describe balance of the randomized treatment groups.

Outcome description and distributional assessment

All prespecified outcomes are quantitative or potentially treatable as such depending on the degree to which their full scales occur in our study population. We will thus describe each initially as indicated above for quantitative baseline variables, overall and by treatment \times time combinations, including visually using grouped boxplots and kernel density estimators. To assess compatibility with the assumptions of the planned analytic approach, for each outcome we will use restricted (equivalently, residual) maximum likelihood (REML) estimation to fit preliminary mixed models with fixed effects of randomized treatment, visit, and their interactions, and with unrestricted covariance matrices -- thus allowing within treatment and visit variability to change over time and accounting for arbitrary correlations between measurements of the outcome in the same patient at different visits. These models will not be used to estimate treatment effects, but only to assess the compatibility of their residuals with the requisite distributional assumptions about random noise to support validity of fixed effect estimates and tests from the planned inferential analyses.

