Once the scale of analysis and analytic approach have been chosen for outcomes incompatible with the prespecified default model, a covariance structure will be selected for each non-multinomial analysis by comparing Schwarz' Bayesian Information Criterion (BIC) after fitting the unconstrained fixed effects model above using the following six choices: time series homogeneous and heterogeneous order one autoregressive AR(1), order one antedependence, homogeneous and heterogeneous compound symmetry, and unrestricted. The homogeneous AR(1) will be considered the default if it yields close to the minimum BIC; otherwise, the structure with minimum BIC will be used. Residuals from the above saturated fixed effects model with the selected covariance structure will then be checked as above to confirm adequacy of the transformation or generalized linear mixed model.

Treatment effect estimation and testing

Assuming required assumptions are reasonably met, missing data will be multiply-imputed with 50 imputations, as described above, after any transformations of all outcomes to the respective scales determined for analysis. Treatment effects will then be estimated and tested by fitting mixed models, also as described above, on the original or transformed scale, but assuming equally spaced visits and linear time effects, to each imputed full data set. Estimates of the annual rate of change of the outcome variable within each treatment group, and of the treatment effect as their difference, with respective standard errors, will be obtained from each imputation and combined over all imputations using Rubin's standard method, yielding overall point estimates of the rates in each group and the difference in rates between the home Peloton-based exercise and usual care groups (i.e., the treatment effect), with respective overall 95% confidence intervals. Statistical significance of the treatment effects and of temporal change within each group will be tested using Wald statistics. Point and interval estimates on a transformed scale will be back transformed and reported and interpreted on the scales of the original measurements as differences between model-fitted (“predicted”) values of the outcomes for participants beginning with the same baseline value of the outcome measure but assigned to the two groups, for a selection of baseline percentiles of the outcome measure (e.g., 5, 10, 25, 50, 75, 90, 95)..

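### The random order of the baseline on and off exams is used in no planned analysis, which costs a little precision on the eight secondary outcomes and leaves within-arm rates that cannot be read as progression alone

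*SAP*

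**What the plan says.** The SAP's Overview states that outcomes are "assessed in randomly ordered on and off Parkinson's medication examinations at baseline", with the later visits at 6 and 12 months done off medication only. The protocol's section on recruitment, screening and randomization says the comprehensive assessments "will be completed at project enrollment (On- and Off-medication), 6 months (Off-medication), and 12 months (Off-medication". It allows about 2.5 weeks for cycle delivery and both initial assessments together. It does not mention random exam order. Neither document gives the order ratio, its link to treatment allocation, or the interval between the two exams.

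Progression in each arm is to be read from the "estimated annual rates of change of off-medication outcome measures, and the treatment groups are to be compared in intention-to-treat analyses of these estimates". Under Treatment effect estimation and testing, mixed models are fitted "but assuming equally spaced visits and linear time effects, to each imputed full data set". The same section adds: "Statistical significance of the treatment effects and of temporal change within each group will be tested using Wald statistics".

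Exam order does not appear in any of the places where it could be used:
- **Preliminary models:** these have "fixed effects of randomized treatment, visit, and their interactions, and with unrestricted covariance matrices".
- **Treatment-effect models:** these replace visit with linear time and add no order term.
- **Imputation predictors:** the only trial-design variables are clinical site and randomized group.
- **Covariate-adjusted sensitivity analysis:** this draws on the listed baseline variables, and order is not among them.
- **Effect modifiers:** order is not listed.

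**The concern.** Each patient's trajectory starts at the off-medication baseline. A patient examined off first meets that battery unpractised, while a patient examined on first has just done the same tests. By months 6 and 12 everyone has had at least two exposures. If the tests have a practice effect, the baseline therefore differs systematically between the two order groups, for a reason that is known and was randomised.

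Two things are at stake. The first is precision: the order difference stays in the residual variance of the change when a recorded factor could remove it. The second is reading: the annual rates within each arm mix disease change with practice, yet the SAP treats them as progression and tests them. The concern is most plausible for the five secondary motor and three secondary non-motor outcomes. It is weaker for MDS-UPDRS III, which is "an assessment of the motor signs of Parkinson's disease by an examiner masked to the participant's treatment group".

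**Working it through.** **Inputs from the documents.** About 250 patients (protocol, Approach) and 1:1 allocation (SAP, Overview), taken as 125 per arm. Visits at 0, 6 and 12 months, linear time. Neither document states a power, SD or effect size, so there is no figure of the plan's own to reproduce.

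**Assumptions.** Exam order is 1:1 and independent of arm. One practice gain p, in SD units of the 12-month change within order group, is taken as 0.2, 0.3 and 0.5. No further gain accrues at later visits.

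**Step 1: how the baseline enters the slope.** With times 0, 0.5 and 1 year and complete (imputed) data, the generalised least squares weights for the slope are (−1, 0, +1). This holds under AR(1) with correlation 0.5, 0.7 or 0.9, and under compound symmetry. The annual rate is then the month-12 score minus the baseline score, so an order effect at baseline enters in full.

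**Step 2: change by order group**, with d the change free of practice and improvement positive.
- Gain retained: off-first d + p, off-second d; mean d + p/2.
- Gain faded: off-first d, off-second d − p; mean d − p/2.

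In both cases the order groups differ by p, so the added variance is p²/4. The mean shift has the same sign and expected size in both arms and cancels in their difference.

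**Step 3: size.** The difference detectable with 80% power when no order variance is present is (1.960 + 0.842) × √(2/125) = 0.354 SD, at two-sided 5%. Unadjusted power is Φ(2.802/√(1 + p²/4) − 1.960).

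| p | Variance factor 1 + p²/4 | SE increase | Power, unadjusted | 250 patients worth | Within-arm shift (±p/2) |
|---|---|---|---|---|---|
| 0.2 | 1.010 | 0.5% | 79.6% | 247.5 | 0.10 |
| 0.3 | 1.0225 | 1.1% | 79.1% | 244.5 | 0.15 |
| 0.5 | 1.0625 | 3.1% | 77.6% | 235.3 | 0.25 |

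Adjusting for order returns power to about 80%. The Holm-Bonferroni steps for the secondary outcomes use stricter levels, but the variance factor is the same. A gain of a full SD would give a factor of 1.25 and power of 70.7%.

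**Step 4: simulation** of 20,000 trials per scenario, p = 0.3 and 0.5, gain retained or faded, no true treatment effect. The mean treatment difference was within 0.0015 SD of zero and type I error was 4.9% to 5.2%. At p = 0.5 with the gain retained, the SE fell from 0.130 to 0.126 with order in the model.

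**Step 5: the within-arm test.** Suppose there is no true change and the gain is retained. At p = 0.2 the shift is 0.10 with SE √(1.01/125) = 0.090. The test then declares improvement with probability Φ(0.10/0.090 − 1.96), about 20%, against a nominal 2.5%. At p = 0.3 the figure is about 38%, and at p = 0.5 about 77%.

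**The case against.** The strongest reply is that benefit is claimed only from between-arm effects. The SAP's outcome hierarchy gives within-arm tests no role, and the usual-care arm absorbs practice common to both arms. The sensitivity section says the planned analyses rely on randomization, and leaving out an arm-independent covariate is a valid choice. Random order even halves the retained shift compared with a fixed off-first order (p/2 against p). All of this stands. It limits the point to precision and interpretation.

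Three stronger readings are tempting, and the documents do not support them.
- **Practice makes exercise look effective.** If order is independent of arm, both arms shift alike and the difference is unbiased, as Step 4 shows.
- **Carry-over from the on exam is counted as slower progression.** Carry-over occurs only in off-second patients, whose baseline it improves. The favourable shift under a retained gain comes from off-first patients, and the sign reverses if the gain fades.
- **Chance imbalance of order between arms is a further harm.** Its variance is p² × 2 × 0.25/125 = 0.004p². The order variance contributes 2 × (p²/4)/125 = 0.004p² to the treatment difference. These are the same quantity, already in the Wald SE.

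It is also fair to object that the practice size and order ratio are assumed. They are, which is why a range is shown.

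What survives the reply is that the SAP does report and test within-arm change as progression, and that a randomised factor acting directly on the baseline is left unused.

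**Conclusion.** The omission is real and minor. For an assumed practice gain of 0.2 to 0.5 SD of the 12-month change, with 1:1 order independent of arm, ignoring order inflates the variance of the treatment effect by about 1% to 6%. Within-arm annual rates move by 0.10 to 0.25 SD, towards improvement if the gain lasts and towards decline if it fades. A flat usual-care rate on a timed or cognitive test is therefore not by itself evidence of stable disease, and a falling one is not by itself evidence of progression.

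A reader might infer that the treatment comparison is compromised, but nothing in the documents supports that. The slope result in Step 1 was checked for AR(1) and compound symmetry only; weights under the other candidate structures may differ. Retest gain would also arise under a fixed exam order, so random order is not itself the fault.

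**What to change.** - Add baseline exam order (off first or off second) and order-by-time to the treatment-effect models for the eight timed, gait and cognitive secondary outcomes. For the rater-scored primary outcome, do this as a sensitivity analysis. Centre the order variable so that each arm's reported rate averages over both orders.
- Add order to the imputation predictors, so that imputed values do not dilute the order-by-time term.
- State how order was assigned, and tabulate it by arm.
- State that within-arm change on these tests is not read as progression alone. This sentence is needed as well as the model terms, because the terms recover precision but leave the averaged rate shifted.

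Reporting within-arm rates from off-second patients only is not recommended. With a pooled order term, the variance of such a rate is σ²/125 + 0.25 × (2σ²/125) = 1.5σ²/125, so its SE is about 22% larger (√1.5 = 1.22). Those patients are not free of later practice or of fading either.

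The cost is one binary variable, which the dates or times of the two baseline exams should supply, one or two degrees of freedom among about 250 patients, and a sentence of interpretation. No new data are needed.

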Leveraging a Widespread Consumer-based Home Exercise Platform: Our previous model of deploying a consumer-based interactive and connected exercise cycle to the home will be leveraged for this trial.²⁷ The Peloton Indoor Cycle (New York, NY) will serve as the platform to deliver the CYCLE exercise protocol and actively measure exercise performance variables. To ensure safety in exercising and understanding of the Peloton, exercise participants will be properly fit to the Peloton. [name] and [name] will be responsible for conducting this fitting session as both have extensive experience in fitting PD patients on exercise cycles. During this session seat height, reach, clipless or platform pedals, etc. will be optimized for comfort and safety in mounting and dismounting the cycle. Patients will complete a tutorial related to using the cycle, heart rate monitor and data transmission. Patients will be informed of their target HRR (Karvonen method: [(220-age)-resting HR] x 60-80% + resting HR) and complete a brief exercise session to ensure they fully understand the exercise requirements and Peloton interface. They will be provided a Garmin activity monitoring device and instructed on its use. Within 10 days of the clinical fitting session, a Peloton cycle will be delivered to the

Outcome Measure	Domain	Comprehensive
Aim 1		
MDS-UPDRS III	Rater-observed PD global motor symptoms	✓
Aim 2		
Nine Hole Peg Test	Upper extremity dexterity	✓
Timed Up & Go & 10M walk	Transfers, turning, gait speed	✓
Postural sway	Postural stability and Balance	✓
Self-reported falls	Prospectively recorded via fall diary	✓
Six Minute Walk Test	Cardiovascular fitness	✓
Aim 3		
Processing Speed	Info processing speed, implicit learning	✓
Visual Memory Test	Episodic Memory	✓
Trail Making Test A & B	Set-switching, attention, working memory	✓
Neuro-QoL	Quality of life questionnaire	✓
MDS-UPDRS I, II, IV	Part I: non-motor symptoms; Part II: self-reported motor symptoms; Part IV: motor complications	✓

patient's home by a certified technician. They will assemble and setup the cycle according to patient-specific fitting specifications. The certified technician will ensure all aspects of the cycle are working properly. The study coordinator will contact the patient within 48 hours of delivery to ensure the system is functioning as intended.

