- iii. Working memory/set switching: the ratio of time to complete the Trail Making Test B to time to complete the Trail Making Test A.

Descriptive/exploratory motor outcomes are:

- i. Cardiovascular fitness: Six Minute Walk Test distance;
- ii. Postural stability:
 - a. Balance Error Scoring System (BESS) double leg area
 - b. Balance Error Scoring System (BESS) tandem area
 - c. Balance Error Scoring System (BESS) double leg volume
 - d. Balance Error Scoring System (BESS) tandem volume
- iii. Total self-reported falls during the one-year observation period.

Descriptive/exploratory non-motor outcomes are:

- i. Movement Disorder Society Unified Parkinson's Disease Rating Scale Part I: Non-Motor Aspects of
- ii. Experiences of Daily Living (nM-EDL)
- iii. Movement Disorder Society Unified Parkinson's Disease Rating Scale Part II: Motor Aspects of Experiences of Daily Living (M-EDL)

iv. Movement Disorder Society Unified Parkinson's Disease Rating Scale Part IV: Motor Complications. The latter two scales are classified as non-motor rather than motor outcomes because they focus on patient-reported experience of functional and social impacts of the effects of motor symptoms rather than on the symptoms themselves.

Analysis Sets

The inferential and safety analysis set will consist of all randomized patients. The descriptive/exploratory analysis set will consist of all randomized patients who complete baseline procedures for initiating randomized treatment and follow-up, and for whom study follow-up is initiated. Descriptions of baseline variables will use all available data in the inferential and safety analysis set. Inferential and safety outcomes will be analyzed using the inferential and safety analysis set in accordance with the strict intention-to-treat principle, under which all randomized patients are included in analyses in accordance with their randomized treatment assignments, regardless of their post-randomization experience including treatment and dropout from treatment or study. Descriptive/exploratory outcomes will be analyzed using the descriptive/exploratory analysis set.

Missing Data

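### The exploratory analysis set depends on completing unlisted start-up procedures, some apparently exercise-only, so exclusions could differ by arm and followed patients could be dropped

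*SAP*

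**What the plan says.** The SAP, Analysis Sets, defines two sets. The first is complete: "The inferential and safety analysis set will consist of all randomized patients". The second, for descriptive/exploratory work, keeps only randomised patients "who complete baseline procedures for initiating randomized treatment and follow-up, and for whom study follow-up is initiated". Outcomes are then assigned to sets:

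- Inferential and safety: "Inferential and safety outcomes will be analyzed using the inferential and safety analysis set in accordance with the strict intention-to-treat principle".
- Exploratory: "Descriptive/exploratory outcomes will be analyzed using the descriptive/exploratory analysis set".

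The SAP, Overview, is broader. It says "Multiple prespecified quantitative outcomes are hierarchically classified as primary inferential, secondary inferential, and descriptive exploratory outcomes", and closes the same paragraph by saying that, for annual rates of change off medication, "the treatment groups are to be compared in intention-to-treat analyses of these estimates". It carves out no tier.

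The SAP does not list the procedures that qualify a patient for the second set. The protocol section on the home exercise platform describes steps for one arm: "exercise participants will be properly fit to the Peloton", followed by a tutorial and a brief practice session. Then: "Within 10 days of the clinical fitting session, a Peloton cycle will be delivered to the" patient's home. Other protocol sections describe steps for everyone, namely the initial on- and off-medication Comprehensive assessments and an activity monitor.

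**The concern.** A set that requires patients to complete the steps for starting their assigned treatment can select on something that happens after randomisation and depends on the assignment. If the exercise arm has more steps to complete, it has more ways to lose a patient from the set. The retained groups may then no longer be the groups that randomisation made comparable.

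The two conditions are joined by *and*. Read literally, a patient who misses a qualifying step but attends the 6- and 12-month visits is left out, although the outcomes were measured.

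At stake are the between-arm comparisons of six-minute walk distance, the balance measures, falls and MDS-UPDRS I, II and IV. The SAP models these much as it models the secondary outcomes. The protocol's outcome table lists the first three under Aim 2 and the MDS-UPDRS parts under Aim 3. Falls deserve the most care: they sit in the restricted set, while safety outcomes are analysed in everyone randomised.

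**Working it through.** The plan attaches no figure to this point: no exclusion rate, dropout rate or outcome SD is given. The check is therefore a comparison of the texts, followed by an illustration on assumed values.

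**Step 1. Which start-up steps belong to which arm (protocol)**

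| Step | Exercise | Usual care |
|---|---|---|
| Initial Comprehensive assessments, on and off medication | yes | yes |
| Activity monitor | yes | yes |
| Cycle fitting, tutorial, practice session | yes | not described |
| Cycle delivery and set-up at home | yes | not described |

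Fitting is assigned to exercise participants and delivery follows it, so both appear to presuppose allocation. The study-flow figure is not available to confirm the order. Whether the SAP counts fitting and delivery among its qualifying procedures is not stated. They are the natural candidates for steps that initiate treatment.

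**Step 2. Whom the rule removes**

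- *Follow-up never initiated.* These patients have no post-baseline exploratory data. Multiple imputation is stated for inferential analyses only, so an available-data analysis of all randomised patients recovers little from them.
- *A qualifying step missed, but followed.* These patients have data and the rule discards them. This is the group that the set definition affects. The documents do not say how many there might be.

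**Step 3. How large the effect could be**

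Inputs from the documents: about 250 patients (protocol) at 1:1 (SAP), so 250 / 2 = 125 per arm. Assumed: p, the share of each arm excluded, and D, the mean difference in SD units between retained and excluded patients.

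Within an arm, the mean of everyone randomised is the retained mean minus p × D, so restriction moves the arm mean by p × D. Hence:

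- shift in the arm difference = (p_ex − p_ucc) × D
- SE = √(1/n_ex + 1/n_ucc); with nobody excluded, √(2/125) = 0.126 SD
- actual error of a nominal two-sided 5% test = 1 − Φ(1.96 − shift/SE) + Φ(−1.96 − shift/SE)

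| Excluded, exercise / usual care | D (SD) | Retained | SE (SD) | Shift (SD) | Shift / SE | Error of nominal 5% test |
|---|---|---|---|---|---|---|
| 2% / 0% | 0.5 | 122 / 125 | 0.127 | 0.010 | 0.08 | 5.1% |
| 5% / 0% | 0.5 | 119 / 125 | 0.128 | 0.025 | 0.20 | 5.4% |
| 10% / 0% | 0.5 | 112 / 125 | 0.130 | 0.050 | 0.38 | 6.7% |
| 15% / 0% | 0.5 | 106 / 125 | 0.132 | 0.075 | 0.57 | 8.8% |
| 10% / 0% | 1.0 | 112 / 125 | 0.130 | 0.100 | 0.77 | 12.0% |
| 10% / 2% | 0.5 | 112 / 122 | 0.131 | 0.040 | 0.31 | 6.1% |
| 0% / 2% | 0.5 | 125 / 122 | 0.127 | −0.010 | −0.08 | 5.1% |
| 2% / 2% | 0.5 | 122 / 122 | 0.128 | 0 | 0 | 5.0% |

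The shift is small unless exclusion is both clearly unequal and strongly prognostic. It vanishes when exclusion is equal and D is the same in both arms. The formula counts every excluded patient as if the outcome could be recovered, so it overstates what a change of set can correct when some of them were never followed.

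**The case against.** The strongest defence is that the restricted set is prespecified in plain sight. Analysis Sets promises strict intention-to-treat only for inferential and safety outcomes and gives the exploratory tier a different set in the same paragraph. A specific section normally governs a summary. The Overview sentence also concerns annual rates of change, so it does not cover total falls, which is a one-year count. This stands: a reader might infer that the SAP breaks its own intention-to-treat analysis, and the documents do not support that. What remains is an Overview sentence that names three tiers and excepts none.

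A reader might also infer that the rule removes anyone who never rides. It does not: it asks for completed procedures, and a patient who completes them and then does no exercise stays in.

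Nor do the documents show that exclusions would fall on the exercise arm alone or favour exercise. The procedures cover follow-up as well as treatment, and both arms have assessments and a monitor to complete. Safe mounting and dismounting, and medical clearance where the screen calls for it, are eligibility conditions for all, so some of those least able to use the cycle are screened out before randomisation. Usual-care patients could equally leave before follow-up begins.

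Finally, the SAP bars benefit claims outside the nine inferential endpoints and bars claims of benefit or harm from exploratory tests. That limits the consequence. It does not remove the selection from estimates, intervals and p-values that may still be reported by arm.

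**Conclusion.** The point holds as a minor one. The exploratory set makes an avoidable selection, possibly after randomisation and possibly unequal between arms, and as worded it discards data from any patient who misses a qualifying step but is followed. It does not match the Overview's unqualified sentence.

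The primary outcome, the eight secondary outcomes and safety are untouched, because they already use everyone randomised. On the assumed 5% to 10% exclusion in one arm only, with D = 0.5 SD, the shift is 0.025 to 0.05 SD, about 0.2 to 0.4 of a standard error. The sign is unknown: it depends on which arm loses more patients and on how they differ from those retained. That some treatment-initiation steps are exercise-only comes from the protocol; that the SAP means those steps is an inference.

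**What to change.** In the SAP, Analysis Sets:

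1. Analyse the descriptive/exploratory outcomes in the all-randomised set already defined, by assigned arm, using all available data. No imputation need be added.
2. Keep the present set, if wanted, as a supportive analysis. List its qualifying procedures, say which apply to each arm, and report the number excluded and the reason by arm.
3. Align the Overview with Analysis Sets so that both state the same scope for intention-to-treat.

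The cost is a few sentences. No new data are needed, and the inferential and safety analyses do not change. With all randomised patients included, the set definition itself contributes no shift. Patients who were never followed remain a missing-data question, which this change does not settle. It is a free improvement.
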